## **Methods:**

**Dual-energy x-ray absorptiometry (DXA):** BMD at the lumbar spine, hip, and radius, as well as lean mass and fat mass, will be assessed by DXA (Hologic 4500, Hologic, Inc., Waltham, MA) with a precision of 0.01 g/cm^2 at the lumbar spine and 1.5% for lean mass .

**Bone Microarchitecture and Micro Finite Element Analysis (μFEA):** *In vitro* strength testing reflects the importance of bone morphology and microstructure in addition to BMD in determining bone strength. DXA cannot provide information about the distinct densities of the cortical and trabecular compartments of bone, the 3D-geometry of bone, or bone microstructure. HR-pQCT assesses these parameters and performs *in vivo* assessment of trabecular architecture and volumetric BMD with very high resolution. We will use the 2nd-generation high-resolution peripheral QCT (HR-pQCT) (XCT-II, Scanco Medical AG®, Bassersdorf, Switzerland) to measure volumetric BMD (vBMD), morphology and microarchitecture at the ultradistal radius and tibia. The variables computed by automated analysis include vBMD (g hydroxyapatite/cm^3) for the total, trabecular, and cortical regions; cortical thickness (μm) and porosity measures; and trabecular number (mm^-1), thickness (μm), and separation (μm).

Measurements will be performed at the non-dominant wrist and leg (if fracture history, the non-fractured side will be used). Using a scout view, the reference line is set at the bone endplate. Scans will be at a distance from the endplate relative to the individual subject's limb length (ultradistal: 7%) to adjust for body size. Each scan includes a stack of 168 slices with an isotropic voxel size of 61  $\mu\text{m}^3$ . Cortical and trabecular compartments are segmented using a fully automatic contouring procedure. The fine structure will be segmented using a simple threshold process. Trabecular (trab) vBMD is calculated as the average mineral density within the trabecular region. Trab bone volume fraction is calculated directly (mineralized bone voxels/ total voxels). Trab thickness,

separation, and number are calculated using the direct 3D distance transformation method. Mean and distribution of intracortical pore diameter is measured by the direct 3D method. Intracortical porosity is calculated as intracortical pore volume/total cortical compartment volume. Cortical tissue mineral density is assessed after exclusion of all resolved pore space and surface voxels to minimize partial volume voxels and is a surrogate of matrix mineralization and microporosity beyond the resolution limit of the scanner.

**Quality control (QC) of scanner:** Included with the system (QRM, Moehrendorf, Germany) is a phantom containing rods of hydroxyapatite (densities of 0, 100, 200, 400 and 800 mg HA/cm^3) embedded in a soft-tissue equivalent resin that is scanned daily and calibrates the scanner, so that X-ray attenuation data can be converted to equivalent HA densities. Images are scored for movement artifact at acquisition (score 1-5; 1 indicating best quality) and repeated for scores>2. Images scored >3 will be excluded. Weekly, a more extensive QC procedure is performed. **Microfinite element analysis (μFEA),** an established analytical engineering technique to estimate stresses and strains induced by mechanical loading of complex structures, will be used to study bone strength. Using HR-pQCT data, it strongly predicts *in vitro* femoral and vertebral breaking strength, and correlates more strongly with failure load than bone mass or structure. *In vivo* test-retest precision is <1.0% for integral, trabecular, and cortical BMD, <2% for trabecular architecture, and <4% for μFEA stiffness and failure load. **Individual Trabeculae Segmentation (ITS):** The trabecular bone compartment is from the HR-pQCT images and will undergo ITS-based morphological analysis. Volumetric decomposition will be performed to derive plate and rod bone volume fraction, number density, thickness, plate surface area, and rod length, topology: plate and rod tissue fraction, and plate–plate, plate–rod, and rod–rod junction density, and orientation, as previously reported.

**Laboratory testing:** IGF-1 will be measured by liquid chromatography/mass spectrometry (LC/MS) (Quest Diagnostics, San Juan Capistrano, CA). Bone markers serum osteocalcin, serum C-telopeptide (CTX) and intact N-terminal propeptide of type 1 procollagen (PINP) will be measured by chemiluminescence assay at Maine Medical Center. 25-OH vitamin D will be measured by LC/MS (Quest Diagnostics, Marlborough, MA). The samples will be deidentified and coded with a unique ID that does not contain any protected health information. The study team will be able to re-identify participants, however, the investigators at Maine Medical Center and Quest will not be able to do so. Samples will be sent via air mail, following IATA shipping guidelines. Materials sent to Maine Medical Center and Quest will not be stored there for further use; extra samples will either be destroyed or sent back to the study team via air mail, following IATA shipping guidelines. If a subject wanted to withdraw their samples from either site before the samples were returned or destroyed, the study team would provide the Maine Medical Center and/or Quest with the subject's deidentified study ID, and the sample would be destroyed without further testing.

**Questionnaires:** Eating-disorder psychopathology will be measured using the Eating Disorder Examination-Questionnaire, a self-report measure of eating disorder severity over the past 28 days along

four dimensions-- restraint, eating concern, shape concern, and weight concern. Subjects will also record current frequency of binge eating and compensatory behaviors on the EDE-Q. The Eating Disorder Inventory will be used to assess three eating-disorder-risk subscales – drive for thinness, bulimia, and body dissatisfaction. Hours of vigorous physical activity per week will be quantified using the Paffenbarger scale. Dietary intake of calcium and vitamin D will be quantified using a food frequency questionnaire.

## VI. Biostatistical Analysis

**Sample Size and Justification:** Group sample sizes of 20 (active therapy) to 10 (placebo) for a total N=30 will achieve 80% power to reject the null hypothesis of equal means when the population mean difference is at least 9% with a standard deviation between groups of 8% and with a significance level of (alpha) of 0.050 using a 2-sided 2-sample equal-variance t-test. This is based on the difference in percent change in spine bone density between the romosozumab (n=65) and placebo (n=61) groups in Cosman F. *et al.*.

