### **III. Subject Selection**

Approximately 75 women will be screened for eligibility in order to identify 30 eligible women with anorexia nervosa, ages 20 to 60, to enroll in the study. Subjects will be randomized in a double-blind fashion to one of two groups for 12 months: monthly 1) romosozumab (210 mg, which must be administered as two injections of 105 mg) or 2) two identical placebo injections to determine effects on BMD, markers of bone metabolism, bone microarchitecture, and bone strength at trabecular and cortical sites. All subjects will meet the DSM-V criteria for AN or atypical anorexia and will be assessed for study suitability and monitored throughout the study period for their overall psychiatric clinical state in coordination with the patients' clinical care team by a study psychologist or psychiatric nurse practitioner.

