**Exclusion Criteria:**

- Hospitalization within 3 months of baseline study visit, including inpatient eating disorder treatment facility; participating in a residential eating disorder treatment program within 3 months of study participation is permitted
- Myocardial infarction or stroke within 1 year preceding enrollment
- History of hypertension or use of anti-hypertensive medications within the past 6 months
- Any disease known to affect bone, including untreated thyroid dysfunction, Cushing's or renal failure
- Any medication known to affect bone metabolism within 3 months of the study, excluding oral contraceptives or other forms of estrogen administration. Bisphosphonates must have been discontinued for at least one year before participation
- Immunodeficiency or taking immunosuppressive therapy
- Serum 25-OH vitamin D level  $<30 \text{ ng/mL}$
- Serum potassium  $<3.0 \text{ meq/L}$
- Serum magnesium  $<1.5 \text{ meq/L}$
- Serum ALT  $>3$  times upper limit of normal
- eGFR of less than 30 ml/min
- LDL  $> 190 \text{ mg/dL}$
- Hypocalcemia
- Diabetes mellitus
- Active substance abuse, including alcohol
- Current smoker
- History of malignancy
- Paget disease of bone
- Osteomalacia

- Osteonecrosis of the jaw (ONJ) or risk factor for ONJ, such as invasive dental procedures (eg, tooth extraction, dental implants, oral surgery in the past 6 months), poor oral hygiene, periodontal and/or pre-existing dental disease, and current use of corticosteroids.
- Planned invasive dental procedure over the next 24 months
- Known sensitivity to any of the products or components of the medication to be administered
- Sensitivity to calcium or vitamin D supplements
- Pregnant, planning to become pregnant within 12 months after the end of treatment and/or breastfeeding
- Subjects with a known esophageal disease
- Abnormalities of the esophagus such as stricture or achalasia
- Inability to sit/stand upright for at least 30 minutes
- Hypersensitivity to any component of zoledronic acid

**Drop Criteria (conditions for withdrawing subjects). These criteria (other than pregnancy) apply until the zoledronic acid infusion has occurred:**

- Pregnancy (for any subject)
- BMI < 16.0 kg/m^2 at two consecutive study visits at which weight and height are measured
- Hospitalization, including inpatient eating disorder treatment facility; participation in a residential eating disorder treatment program is permitted

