- Medical instability, which will be determined by the study physician. Patients in this category will be assessed by the Data Safety Monitoring Board and continue to be assessed according to study protocol.
- Serious study-related adverse event

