#### **IV. Subject Enrollment**

Informed consent will be obtained from all potential study subjects by a licensed physician investigator or nurse practitioner investigator before any procedures are performed. At this time, the subject will be explicitly counseled that she is free to choose whether or not to participate in this study.

Eligible subjects will be randomized at the baseline visit to the treatment or placebo group. Neither the investigator nor the subject will be aware to which group she is assigned until after the study is completed and has been un-blinded or in the case of significant safety considerations for a specific subject.

All subjects will receive a single intravenous infusion of open-label zoledronic acid at the month 12 study visit.

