7. Plain film of wrist/hand to determine bone age in women with primary amenorrhea who have not received estrogen for  $\geq 1$  year.
8. Electrocardiogram (ECG or EKG) to assess cardiovascular risk.

If the 25-OH vitamin D level at the screening visit is not  $>30$  ng/ml, participants will be given one loading dose of oral vitamin D3 (cholecalciferol) 5,000 IU daily and the 25-OH vitamin D level will be checked every 3 weeks until their 25-OH vitamin D level meets the eligibility requirement ( $>30$  ng/ml).

**Baseline Visit:** Eligible study subjects (n=30 women with anorexia nervosa or atypical anorexia) will be assessed at an outpatient visit at MGH for baseline testing.

1. A clinical and bionutrition evaluation and urine pregnancy test (unless exempt from urine hCG).
2. DXA scan of the spine, hip, radius, and total body for BMD and body composition, including lean mass, if screen visit did not take place within 6 weeks of baseline visit or if a DXA scan was not performed at the screening visit.
3. Baseline hormone and safety blood testing, if not performed clinically within 2 weeks prior to the baseline visit.
4. HR-pQCT and FEA of the radius and tibia
5. Eating Disorder Examination—Questionnaire
6. Eating Disorder Inventory-3
7. Paffenbarger Exercise Questionnaire
8. Calcium and vitamin D food frequency questionnaire

Randomization to treatment or placebo group will occur at the baseline visit. Twenty subjects will be randomized to active romosozumab (210 mg, which must be administered as two injections of 105 mg) and 10 subjects will be randomized to identical placebo injections. In the rare case that a subject withdraws from the study after being randomized but prior to completing the baseline visit, we will replace such dropouts with the goal that thirty subjects will complete the baseline visit. Randomization will be stratified for presence or absence of atypical anorexia nervosa, defined as  $BMI \geq 18.5$  kg/m^2 vs.  $< 18.5$  kg/m^2. Subjects will return every month over the following 12 months to receive ongoing injections.

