### **Data Analysis Plan:**

The data analysis plan for the study will be as follows. The primary analysis will be intention-to-treat, with the primary endpoint being change in PA lumbar spine aBMD. Statistical significance will be defined as a two-tailed p-value of  $\leq 0.05$ .

Phase 1 Aims 1-3: Baseline mean clinical characteristics between the 2 groups will be compared by t-test. Variables will be tested for normality using the Shapiro-Wilk test, and if non-normal, variables will be log-transformed before analysis. If the distribution remains non-normal after log-transformation, nonparametric testing using the Wilcoxon rank sum test will be performed instead. The analysis of variables at 12 months will be performed using a linear random effects model to estimate and test the effects of the 2 randomization groups (romosozumab vs placebo) from baseline to 12 months on the study endpoints.

Phase 1 Aim 4: The analysis of variables at 12 months will be performed using a linear random effects model to estimate and test the effects of the 2 randomization groups (romosozumab vs placebo) from baseline to 12 months on the study endpoints. We will also add a lean body mass x randomization group interaction term to examine if the effects of body mass change differ between romosozumab and placebo.

Phase 2 Aim 1: The analysis of variables at 24 months will be performed using a linear random effects model to estimate and test the effects of the 2 randomization groups (12 months of romosozumab followed by a single intravenous infusion of open-label zoledronic acid vs 12 months of placebo followed by a single intravenous infusion of open-label zoledronic acid) from baseline to 24 months on the study endpoints.

Phase 2 Aim 2: A secondary analysis will be performed to determine whether gains achieved in the romosozumab group are maintained through the subsequent 12-month study period using a linear random effects model with the fixed effect being time and the random effect being the intercept. Lack of statistical significance will indicate maintenance (lack of decrease--or increase) of BMD.

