**Atypical femoral fractures.** An atypical femoral fracture is an unusual thigh bone fracture that may occur with little or no trauma. Fractures can occur in both thighs at the same time. Atypical fractures have been reported rarely in patients receiving romosozumab. It is unknown whether the risk of atypical femoral fracture continues after stopping therapy. It can present with new or unusual hip, thigh, or groin pain weeks to months before the fracture is diagnosed. Subjects will be instructed that if they develop any of these symptoms, they should report them to the study doctor and the physician they see for clinical care. Patients presenting with an atypical femur fracture will also be assessed for symptoms and signs of fracture in the contralateral limb.

In clinical studies, after romosozumab discontinuation, BMD returns to approximately baseline levels within 12 months in the absence of follow-up antiresorptive therapy. This is why we propose to follow the 12 months of romosozumab or placebo with a single intravenous infusion of open-label zoledronic acid at the 12-month visit.

The potential effects of romosozumab on the fetus are not known, and therefore precautions against administration to pregnant patients will be instituted. All patients will have pregnancy tests on admission prior to receiving study medication and serial pregnancy tests at every study visit and will be required to use contraception in order to participate in the protocol (unless exempt). Any subject who becomes pregnant during the course of the study and is discharged from participation, will undergo a follow-up study visit. This will include assessment by an MD or NP for study medication related side effects, including hypocalcemia, and measurement of a calcium level if it has not been done clinically.

After patients start taking romosozumab, it is possible that their body may make antibodies to romosozumab. Antibodies to romosozumab have not been associated with changes in the efficacy or safety of romosozumab.

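### Should the sample size section allow for women who have no month-12 spine DXA?

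*Combined protocol and SAP*

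**What the plan says.** The Sample Size and Justification paragraph (section VI) sets groups of 20 on active therapy and 10 on placebo, a mean difference of 9% in percent change in spine bone density, a standard deviation of 8%, and a two-sided equal-variance t-test at 0.05. It states that these groups, "for a total N=30 will achieve 80% power to reject the null hypothesis of equal means". It gives no expected loss.

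Section III, Subject Selection, plans to screen about 75 women "in order to identify 30 eligible women with anorexia nervosa, ages 20 to 60, to enroll in the study". Section V (Baseline Visit) randomizes 20 and 10, the same numbers as in the power calculation. Replacement is limited to a woman who "withdraws from the study after being randomized but prior to completing the baseline visit, we will replace such dropouts".

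On withdrawal, the Drop Criteria list pregnancy, low BMI at two consecutive measured visits, hospitalization, medical instability and serious study-related adverse events. "These criteria (other than pregnancy) apply until the zoledronic acid infusion has occurred", and under section IV, "All subjects will receive a single intravenous infusion of open-label zoledronic acid at the month 12 study visit". For medical instability the text adds: "Patients in this category will be assessed by the Data Safety Monitoring Board and continue to be assessed according to study protocol". For pregnancy, section VII says: "Any subject who becomes pregnant during the course of the study and is discharged from participation, will undergo a follow-up study visit". The listed content of that visit is a side-effect assessment and a calcium level.

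The Data Analysis Plan says: "The primary analysis will be intention-to-treat, with the primary endpoint being change in PA lumbar spine aBMD". The model is a linear random effects model. Section V schedules DXA at 6 and 12 months in Phase 1.

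**The concern.** The number analysed in the power calculation equals the number randomized, and the primary endpoint is read a year later. In that year the protocol itself lists several reasons to withdraw a woman, and no loss after the baseline visit is made up. The stated 80% would then be the best case. The placebo arm is the sensitive one, because with only 10 women each missing scan costs more there than in the romosozumab arm.

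The background section praises the low drop-out in the team's ongoing pilot of another drug but gives no figure, so a reader cannot tell what power the sponsor really expects. If losses were sizeable, a non-significant result might be read against 80% power when the true figure was nearer 70%.

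**Working it through.** **Inputs.** From Sample Size and Justification: n1 = 20, n2 = 10, difference 9, SD 8 (read as the common within-group SD), two-sided 0.05. The 9% and 8% come from a cited trial that was not available, so they are taken as given.

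**Formula.** Noncentral t with df = n1 + n2 − 2 and noncentrality = 9 / [8 × √(1/n1 + 1/n2)].

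**The plan's own figure.** √(1/20 + 1/10) = 0.3873, so the standard error is 8 × 0.3873 = 3.098. Noncentrality is 9 / 3.098 = 2.905 on 28 df, and power is 80.06%. The difference detectable with 80% power is 8.99%. The stated 80% reproduces, with no margin.

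**If month-12 scans are missing.** The documents give no rate, so the evaluable numbers below are assumptions. The same formula on completers gives:

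| Evaluable (romosozumab : placebo) | Standard error | Noncentrality | df | Power | Detectable difference at 80% power |
|---|---|---|---|---|---|
| 20 : 10 | 3.098 | 2.905 | 28 | 80.1% | 9.0% |
| 19 : 10 | 3.125 | 2.880 | 27 | 79.3% | 9.1% |
| 18 : 10 | 3.155 | 2.852 | 26 | 78.4% | 9.2% |
| 20 : 9 | 3.211 | 2.803 | 27 | 77.1% | 9.3% |
| 18 : 9 (10% loss) | 3.266 | 2.756 | 25 | 75.4% | 9.5% |
| 16 : 8 (20% loss) | 3.464 | 2.598 | 22 | 70.0% | 10.2% |

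**Credit for the month-6 DXA.** The random effects model can use the month-6 scan of a woman who misses month 12. Suppose every such woman has that scan, data are missing at random, and the 6- and 12-month changes correlate at r = 0.5 to 0.8 (assumed; the documents give no correlation). Then the variance of an arm's month-12 mean is approximately 64 × [(1 − r²)/completers + r²/randomized], with df = completers − 2.

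- 18 : 9, r = 0.5: 64 × [0.75 × (1/18 + 1/9) + 0.25 × (1/20 + 1/10)] = 64 × 0.1625 = 10.40. Standard error 3.225, noncentrality 2.791, power 76.5%.
- 18 : 9, r = 0.8: 64 × [0.36 × 0.16667 + 0.64 × 0.15] = 64 × 0.156 = 9.984. Standard error 3.160, noncentrality 2.848, power 78.2%.
- 16 : 8, the same steps: 72.2% (r = 0.5) to 75.8% (r = 0.8).

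So with 10% loss the shortfall from 80.1% is about 2 to 4 points (80.1 − 78.2 = 1.9; 80.1 − 76.5 = 3.6).

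**Are withdrawn women unscanned?** The Drop Criteria say when a woman is withdrawn. They do not say that her month-12 DXA is cancelled, and the primary analysis is by intention to treat. For medical instability the text says that assessment continues; for pregnancy it describes one visit with no DXA listed; for the other reasons it is silent. The low-BMI rule needs two consecutive visits with weight and height. After baseline, Phase 1 takes these at months 3, 6, 9 and 12, so a woman who meets the rule will often have reached the month-6 scan.

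**The case for a change.** The strongest case for a change is that the section makes a formal power claim for a hypothesis test and so should state the condition on which it rests. One or two sentences would do it, at no cost in patients or procedures. The team also has an ongoing pilot from which a rate could be taken. Neither the model nor intention-to-treat fully rescues the figure: power stays below 80% in every loss scenario above, the month-6 credit needs a month-6 scan and data missing at random, and the plan states no missing-data assumption. Nor are the completer figures a strict floor, because women who stop injections but are still scanned can dilute the difference.

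Much of this stands as description. The allowance for loss is absent, and stating it would be good practice. But dilution is a question about the 9% input and not about missing scans, and that input may already reflect non-adherence in the trial it came from. The pilot's low drop-out was attributed to less frequent dosing, so its rate may not carry over to monthly injections. The condition is not hidden either: the 80% is tied in the same sentence to 20 and 10, and any reader can recompute it for other numbers. What remains is a missing sentence about expectation; no stated number is wrong.

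**Conclusion.** No change follows. The 80% is correct for 20 and 10 evaluable women, and the paragraph names those numbers. The gap is real but small: no anticipated loss is stated, and replacement ends with the baseline visit. On assumed losses, t-test power would be 79.3% or 77.1% with one woman missing (romosozumab or placebo), 75.4% at 10% loss and 70.0% at 20%. The planned model recovers part of this if month-6 scans exist and data are missing at random. Every shortfall rests on a loss rate or correlation that the documents do not give.

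The study is titled a pilot. Adding the sentence would not alter the sample size, the schedule, the endpoint or the analysis, and the treatment comparison is no less valid without it. When results are reported, the confidence interval for the 12-month difference will show the precision achieved with the women actually scanned, which serves a reader better than a revised forecast of power.
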